8.3 Tissue Sample for STAT3 Crosslinking

If possible, we would like to quantify the photoreaction using an assay that will evaluate the signal transducer and activator of transcription 3 (STAT3) crosslinking that we have shown to be associated with durable response of early stage HNSCC treated with external beam PDT (1). For performing the STAT3 assay, the treating physicians will use the EBUS (if performed as well) to collect 1 to 5 tumor tissue biopsies (about 100-300 mg per biopsy, if feasible) from the treated area immediately (within minutes) **after** I-PDT. These research biopsies will be snap-frozen on dry ice and processed for determining STAT3 cross-linking as previously described (2, 3). Immunoblot signals for STAT3 will be quantified and expressed as percent conversion of monomeric into covalently cross-linked dimeric STAT3.

Samples will immediately be frozen at -70°C until analyzed. Samples will be processed, stored, and analyzed in [name] laboratory (same location).

[name], D.Sc. Roswell Park Comprehensive Cancer Center PDT Center Medical Research Complex (MRC) M-156 Attn: Study Number I 279415 [name] Office [contact] Off hours contact number (cell): [contact] [contact]

EXTERNAL (NETWORK) SITES: Follow directions above for sample collection and processing (Note: External sites will process samples as personnel will be cross trained for uniform sample processing.). The cryogenic tubes will be labeled with the Subject ID #, initials, the participant's study number, clinical study number, protocol time point, dose, and protocol day. The samples will immediately be frozen at -70°C or below (samples are to be stored until requested for batch mailing). Samples are to be batch shipped, frozen, on dry ice.

Roswell Park External Site Coordinators must be notified by email on the day prior to sample shipment at [contact].

Frozen samples will be shipped via Fed Express Overnight on dry ice with delivery on Mon.-Fri., NO SATURDAY DELIVERY. Do not ship on a Friday or the day before a holiday.

Address shipments to the address provided above. For any questions regarding specimen processing contact [name], [contact]) or email: [contact].

Note: All investigator or analyzing research laboratories housing research samples need to maintain current **Temperature Logs** and study-specific **Sample Tracking and Shipping Logs**. The Principal Investigator/Laboratory Manager **must** ensure that the stated lab(s) have a process in place to document the receipt/processing/storage/shipping of study-related samples/specimens. This is required for both observational and interventional clinical studies collecting clinical samples.

8.4 Blood Draw and Tissue Samples for Immune Markers

Recent work from the [name] lab has demonstrated the critical role of the immune system in PDT efficacy. Because of the importance of the immune system for PDT efficacy, along with the potential for the immune system to mount an effective anti-tumor response, it would be beneficial to monitor immune markers (detailed in the last paragraph of **Section 1.9**) for correlation between the I-PDT and/or PDT treatment and local or distant disease recurrence.

Blood samples will be collected via venipuncture for immune marker analysis. Samples will be collected using 3, 10 mL heparinized green-top collection tubes. Tumor tissue samples (50-300 mg per biopsy) will be collected during the endoscopy procedure using the EBUS needle.

Samples for immune marker analysis will be obtained on:

- Blood samples prior to the administration of the porfimer sodium and on the day of porfimer sodium administration.
- Tumor tissue and blood sample prior to the laser light illumination and on the day of I-PDT and/or PDT.
- 7-10 days following I-PDT and/or PDT with bronchoscopy procedure.
- Initial follow-up (approximately 4 weeks ± 1 week following last I-PDT and/or PDT with bronchoscopy)

Whole blood samples (3 tubes) and fresh tissue samples (in saline) will be sent the same day of collection, to the Flow Cytometry Department for processing.

[name] Department of Flow and Image Cytometry Cancer Cell Center C-311 Attn: Study Number I 279415 [name] Office [contact] Laboratory [contact] [contact]

EXTERNAL (NETWORK) SITES: Follow directions above for sample collection and processing (Note: External sites will process samples as personnel will be cross trained for uniform sample processing.). The cryogenic tubes will be labeled with the Subject ID #, initials, the participant's study number, clinical study number, protocol time point, dose, and protocol day. The samples will immediately be frozen at -80°C or below (samples are to be stored until requested for batch mailing). Samples are to be batch shipped, frozen, on dry ice.

Roswell Park External Site Coordinators must be notified by email on the day prior to sample shipment at [contact].

Frozen samples will be shipped via Fed Express Overnight on dry ice with delivery on Mon.-Fri., NO SATURDAY DELIVERY. Do not ship on a Friday or the day before a holiday.

Address shipments to the address provided above. For any questions regarding specimen processing contact [name], [contact] or email: [contact].

Note: All investigator or analyzing research laboratories housing research samples need to maintain current **Temperature Logs** and study-specific **Sample Tracking and Shipping Logs**. The Principal Investigator/Laboratory Manager **must** ensure that the stated lab(s) have a process in place to document the receipt/processing/storage/shipping of study-related samples/specimens. This is required for both observational and interventional clinical studies collecting clinical samples.

8.4.1 Pathology

Standard pathologic analysis of resected lung tissue will be performed. The electronic health records (EHR) will be used to review and collect information from the cytology report.

9 EFFICACY EVALUATIONS

9.1 **Objective Tumor Response**

All protocol-defined imaging studies must be performed at the investigative site or sponsorapproved facility using protocol-defined parameters. The same method of assessment and the same technique should be used to characterize each identified and reported lesion at baseline and during follow-up. A modified RECIST 1.1 criterion will be used to assess objective tumor response of the I-PDT and/or PDT treated tumor.

RECIST 1.1 will be used for tumor response assessment at time of continuing review and will be used for IRB reporting and formal analysis.

Along with tumor size and volume, percent of airway obstruction (in cases where an airway stent is not placed) measured by bronchoscopy, will also be used as a measure of tumor response.

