4 METHODOLOGY

4.1 Study Design

This is a multi-center, multi-arm, Phase I (Cohort 0; data collection complete) to monitor the safety and Phase II study (Cohort A and Cohort B described below) to monitor the efficacy of EBUS-

TBN guided I-PDT and/or I-PDT and/or PDT in patients with malignant airway obstructions that are refractory to curative chemoradiation or, who are not candidates for curative chemoradiation. Participants will be treated on an outpatient or inpatient basis, and the treating physician will make this decision on a case-by-case basis.

Cohort 0 is closed to accrual and fulfilled the Phase 1 safety monitoring requirements. Cohort 0 provided the safety monitoring component for Cohort A of this Phase II study. Cohort 0 consisted of patients with the diagnosis of lung cancer that received porfimer sodium with EBUS I-PDT and participated in all of the study procedures except the Quality of Life Questionnaires and Six Minute Walk Test.

Cohort A (n=18, Phase II) consists of patients with a diagnosis of lung cancer or other malignancies causing airway obstruction or inoperable malignancies not candidates for curative radiotherapy within the airway; and that receive EBUS I-PDT and all of the study procedures. Subjects treated in Cohort 0 are considered the Phase I part of Cohort A.

Cohort B (n=39) will consist of patients with the diagnosis of lung cancer or other malignancies causing airway obstruction, or inoperable malignancies not candidates for curative radiotherapy within the airway. Subjects in Cohort B will receive the EBUS-guided I-PDT 48 ± 4 h after standard of care palliative radiotherapy of 8 Gy x1.

NOTE: Given the nature of this advanced airway procedure, only the physician performing the procedure will be the consenter for the procedure as well as for the study.

All participants will undergo the standard of care interventional bronchoscopy procedure with an attempt to treat and resolve the airway obstruction using conventional methods such as mechanical debulking, tumor ablation, and/or airway stenting. Airway stenting will be performed before or after I-PDT and/or PDT, as necessary. Curvilinear EBUS with Color Doppler will be used to guide the intra-tumor fiber insertion.

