- The laser fiber will be placed within the target tumor under EBUS guidance in one to 10 locations, sequentially. The number and location of the fiber placement will be according to a pre-treatment planning (as much as possible), as the example shown in **Figure 3**.

- If possible (i.e., optional), optical measurement of light transmission and tumor pO2 will be performed before and after I-PDT as described in **section 1.1.13**
- Using either fiber, a 630-nm laser light will be administered with the objective to deliver a minimal irradiance of ≥ 8.6, ≥ 10.8 or ≥ 15.3 mW/cm² to a significant volume of the target tumor, based on Oakley et al. 2019. The treatment time will be adjusted to deliver ≥ 45 J/cm² to a significant volume of the target tumor. The research team will present a table showing the light delivery options and percent of tumor volume that will receive the minimal irradiance and fluence for the physician to review.
- The pre-treatment plan will be presented to the treating physician (the investigator) for review and approval. The investigator will decide how many insertions will be made and where the fiber(s) will be inserted, using clinical judgment and taking into account the patient's safety.
- The I-PDT procedure should be complete within a few hours.
- Airway stenting will be performed after I-PDT, as needed.
 - For cases where airway stenting is indicated to secure the airway, EBUS will be performed before or after airway stenting, as necessary, and the identified portion of the tumor will be evaluated and treated with I-PDT.

At least one tumor will be treated during the I-PDT. The treating physician will determine how many tumors will be treated, taking into account the patient's safety.

6.1.3 Endobronchial tumors that are identified with endoscopy and prior CT or MRI will be treated with I-PDT and/or PDT

- The laser fiber will be placed in the tumor for I-PDT or in the airway for PDT.
- A 630-nm laser light will be administered with the objective to deliver a minimal irradiance of ≥ 8.6, ≥ 10.8 or ≥ 15.3 mW/cm² to a significant volume of the target tumor, based on Oakley et al. 2020. (41) The treatment time will be adjusted to deliver ≥ 45 J/cm² to a significant volume of the target tumor. The research team will present a table showing the light delivery options and percent of tumor volume that will receive the minimal irradiance and fluence for the physician to review.

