8.1.11 Schedule of Procedures and Observations

The schedule of procedures and observations for this study is summarized in Table 1 below.

Evaluation	Baseline ¹	Day -3	Day -2	Day -1	Scheduled EBUS I- PDT (Day 0)	Days 1 through 3	Days 2 through 10 ²²	7-10 Days Post- Procedure	Initial Follow-Up ² Evaluation	Long Term Follow-Up ³ Evaluation s
Medical History	Х									
Pre-Existing Conditions	Х									
Physical Examination, including vital signs ⁴	Х				X ⁵		X ^{5,22b}		X	Х
Hematology ⁶	Х		X ²⁴		X ²⁴				X	
Blood Chemistry/creatinine clearance ⁷	Х		X ²⁴		X ²⁴				X	
Pregnancy Test (Urine/Serum)	X^8									
ECOG Performance Status (Appendix A)	Х								X	Х
Tumor/Disease Assessment: Contrast Enhanced CT scan (chest) ⁹ (non-contrast CT if the patient has allergy to the contrast agent)	X9								X9	X9
Injection of porfimer sodium			X							
Diet prior to I-PDT procedure					X ²⁰		X ^{20a}			
Cohort B Only: SOC palliative radiotherapy			X ²²							
SOC Bronchoscopy/EBUS- TBNA					X ¹⁰				X ¹¹	
EBUS color Doppler to identify vasculature					Х					
Tumor Debulking, Ablation and/or Airway Stenting					Х		X			

Table 1Schedule of Procedures and Observations

Evaluation	Baseline ¹	Day -3	Day -2	Day -1	Scheduled EBUS I- PDT (Day 0)	Days 1 through 3	Days 2 through 10 ²²	7-10 Days Post- Procedure	Initial Follow-Up ² Evaluation	Long Term Follow-Up ³ Evaluation s
If possible, optical and pO2 measurements immediately before and after I-PDT					X ²³					
I-PDT ¹² guided with EBUS- TBN and/or I-PDT and/or PDT					X					
Immune marker blood and tumor tissue sampling ¹³			X		Х			Х	Х	
Pre-I-PDT and/or PDT tissue sample					X ^{14,14a}		X ^{14b}		X ¹⁴	
Concomitant Medications	X ¹⁵				Х		X ^{22b}		Х	X ¹⁶
Adverse Events					X		X ^{22b}		Х	
Quality of Life Questionnaire (Appendix D) ¹⁷	Х								Х	X ¹⁸
Six-Minute Walk Test ²¹	Х									X ¹⁸
Survival Status										X ¹⁹

1 Performed within 4 weeks prior to scheduled EBUS I-PDT, as part of standard of care for the therapeutic bronchoscopy, unless otherwise indicated.

2 Initial Follow-Up evaluation at 4 ± 1 weeks after the last I-PDT and/or PDT treatment (dependent on severity of disease and clinical condition of patient).

3 Long-Term Follow-Up routine will be performed only when clinically indicated, at these visits: 8 weeks (± 2 weeks), 12 weeks (± 2 weeks), and 24 weeks (± 4 weeks) after the last I-PDT and/or PDT.

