4 Vital signs: temperature, heart rate, respiratory rate, blood pressure, body weight, and height. *Height collected at baseline only*.

5 To be performed prior to procedures as SOC and at post-operative evaluation after undergoing treatment. Note: on the day of scheduled bronchoscopy, weight is not needed at the preoperative and post-operative physical exam. Oxygen saturation to be measured pre- and post-operatively.

6 Standard of care - will be performed if indicated by the anesthesia pre-op assessment: Complete blood count (CBC) with automated differentials: WBC, RBC, HGB, HCT, platelet, MCV, MCH, MCHC, % neutrophils, absolute neutrophils, % monocytes, absolute monocytes, % eosinophils, absolute eosinophils, absolute basophils, % lymphocyte, absolute lymphocyte, platelet confirmation (as clinically indicated), and differential confirmation (as clinically indicated).

7 Standard of care - will be performed if indicated by the anesthesia pre-op assessment: Complete metabolic panel (CMP): chloride, CO₂, potassium, sodium, BUN, glucose, calcium, creatinine, total protein, albumin, total bilirubin, alkaline phosphatase, AST, ALT, A/G ratio, BUN/creatinine ratio, osmol (Calc), anion gap.

8 Within 7 days prior to study treatment. Serum HCG will be obtained if urine is not available.

- 9 CT scan will be within 2 weeks ± 1 week prior to study treatment. CT scan in Follow-Up, will be performed only when clinically indicated, at these visits: 4 weeks (±1 week), 8 weeks (±2 weeks), 12 weeks (±2 weeks), and 24 weeks (±4 weeks) after the last I-PDT and/or PDT.
- 10 Bronchoscopy (SOC) with EBUS-TBNA. The details of the interventional bronchoscopy procedure described in Section 6.1.2 are standard of care and, do not need to be documented in the Case Report form.
- 11 Schedule date/time for initial follow-up SOC bronchoscopy **without** EBUS-TBNA: TBNA will be performed only if clinically indicated outside the scope of this study. *Note*: Initial follow-up bronchoscopy will be performed within 4 weeks following the initial follow-up visit.
- 12 I-PDT and/or PDT will be performed with 630-nm light delivered through a cylindrical diffuser that will be inserted into tumor through a TBN with EBUS guided imaging. Endobronchial tumors can be treated with I-PDT and/or PDT. An endoscope will be used to guide the fiber placement.
- 13 Refer to Section 8.12
- 14 Refer to Section 8.13 for standard of care Pathology procedures.

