9.2.3 Evaluation of Airway Obstruction

The estimated percentage of obstruction will be documented before and after endobronchial debulking and ablation. Tumor debulking and ablation will always be performed before EBUS-TBNA. The airway obstruction severity is usually estimated based on the size of scope that can be passed through an obstructed airway and based on the size of the balloon used to dilate the obstructed airway.

Airway obstruction severity will be classified as follows (51):

- Mild (<50%),
- Moderate (50-70%) and,
- Severe (>70%).
- The baseline obstruction to be used in the study will be the airway obstruction that was established after debulking and ablation and, before the EBUS-TBN guided I-PDT, and/or I-PDT and/or PDT.

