12.1.3 Primary Phase II Efficacy Analysis

The primary endpoint for Cohort A and Cohort B is the proportion of complete responders (CR) and partial responders (PR) as measured by RECIST v1.1 at 12 ± 1 week after DOSIETM (Cohort A) and COMSOLTM guided I-PDT.

For Cohort A, we hypothesize that the objective tumor response for CR+PR will be at least 29%. We also want to investigate the impact of variation in optical properties, Photofrin® retention, and fiber location perturbation on the objective tumor response. The primary analysis will consist of a one-sided exact binomial test of H₀: π =0.05 versus H_a: π >0.05 at level α =0.05, where π is the proportion of CR+PR responders. For Cohort B, the primary analysis will consist of a one-sided exact binomial test of H₀: π =0.30 versus H_a: π >0.30 at level α =0.05.

Additional clinical efficacy endpoints are: (1) changes from baseline to 3 months in the FACT-L Total Score related subscales (physical well-being, social/family well-being, emotional well-being, functional well-being); (2) the 6-minute walk measures (distance, VO2max, shortness of breath scores). All key clinical efficacy outcomes will be considered suitably continuous will be analyzed with an analysis-of-covariance (ANCOVA) approach regressing change from baseline to three months on the baseline value of the respective measure adjusted for baseline tumor volume, age, and sex.

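### Airway obstruction counts as a response measure only in patients without a stent, so patients stented after the procedure day for a blocked airway drop out and this supportive result can be biased upward

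*Combined protocol and SAP*

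**What the plan says.** Section 9.1 of the combined protocol and SAP assesses treated tumors by modified RECIST 1.1 and names RECIST 1.1 for the formal analysis. It then adds a second reading, the percentage of the airway that is obstructed: "in cases where an airway stent is not placed) measured by bronchoscopy, will also be used as a measure of tumor response". The restriction has no time window and gives no reason for the stent.

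Stenting is foreseen at several points:

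- Section 4.1 has every participant undergo interventional bronchoscopy "with an attempt to treat and resolve the airway obstruction using conventional methods such as mechanical debulking, tumor ablation, and/or airway stenting", and adds: "Airway stenting will be performed before or after I-PDT and/or PDT, as necessary".
- Section 6.1.2 says "Airway stenting will be performed after I-PDT, as needed". Section 6.1.3 has a matching sentence for endobronchial tumors.
- In Table 1 (Section 8.1.11), the row "Tumor Debulking, Ablation and/or Airway Stenting" is marked on Day 0 and again in the Days 2 through 10 column.

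On the starting value, Section 9.2.3 says "The baseline obstruction to be used in the study will be the airway obstruction that was established after debulking and ablation" and before the light treatment. Section 4.1 says only that it is the obstruction before I-PDT and/or PDT. Neither statement mentions a stent already in place.

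On recording, footnote 10 of Table 1 says that the details of the interventional bronchoscopy described in Section 6.1.2 "are standard of care and, do not need to be documented in the Case Report form".

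The primary Phase II endpoint in Section 12.1.3 is "the proportion of complete responders (CR) and partial responders (PR) as measured by RECIST v1.1". Airway obstruction is absent from the endpoint lists in Sections 4.1.2, 4.1.3 and 12, and it has no response threshold, test or sample size.

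**The concern.** A stent is one of the plan's own means of resolving obstruction. Sections 1.1.1 and 2 describe patients whose obstruction tends to recur and who then need repeat palliative procedures, and Section 8.1.8 allows further bronchoscopies as clinically indicated. A stent placed some time after I-PDT can therefore be a sign that the treated airway stayed or became blocked. Under Section 9.1 that patient is removed from the obstruction measure by an event that follows treatment and is tied to the outcome. What remains is the result among patients who did not need a later stent.

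The rule also treats two different cases alike. A stent placed before or during the procedure to secure the airway reflects initial severity. A stent placed later for residual or recurrent obstruction reflects what happened after treatment.

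At stake is the only bronchoscopic response measure in a trial whose title aim is palliation of cancer obstructing the airway. Each cohort is analyzed on its own, so no concurrent control would reveal the selection, and Section 12.1.4 says the data will inform a randomized Phase IIb trial.

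**Working it through.** **Is there a plan figure to reproduce?** None for obstruction. The planned figures concern CR+PR only. By exact binomial calculation:

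- Cohort A (n=18, null 0.05, one-sided 0.05): reject at 4 or more responses; exact alpha 0.0109; power 0.812 at 0.29.
- Cohort B (n=39, null 0.30, one-sided 0.05): reject at 17 or more responses; exact alpha 0.0500; power 0.832 at 0.50.

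Both meet the stated power of 0.80. Neither depends on obstruction or stents. Section 9.2 has all treated tumors measured on CT, and Section 12.1.3 contains no stent exclusion.

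**Size of the selection.** Take the patients who leave the Day 0 session without a stent, and let

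- p = the proportion of them whose obstruction improves, if all are counted;
- s = the share stented later;
- r = the proportion of those stented later who count as improved.

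Dropping the later-stented patients gives

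observed rate = (p − s·r) / (1 − s), so bias = s·(p − r) / (1 − s).

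Three cases follow:

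- r = 0 (every later stent marks a failure): observed rate = p / (1 − s).
- r = p/2: observed rate = p·(1 − s/2) / (1 − s).
- r = p (stenting unrelated to response): observed rate = p, so no bias.

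The documents give neither s nor p. The ranges below are assumptions.

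| s | 1/(1−s) | p=30%, r=0 | p=30%, r=p/2 | p=50%, r=0 | p=50%, r=p/2 |
|---|---|---|---|---|---|
| 10% | 1.11 | 33.3% | 31.7% | 55.6% | 52.8% |
| 20% | 1.25 | 37.5% | 33.8% | 62.5% | 56.3% |
| 30% | 1.43 | 42.9% | 36.4% | 71.4% | 60.7% |
| 40% | 1.67 | 50.0% | 40.0% | 83.3% | 66.7% |

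For example, at s = 20%, p = 30% and r = 0: 0.30 / 0.80 = 0.375.

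**Does anything in the plan correct this?** No section separates stents by timing or reason, counts a later stent as a failure, or gives a missing-data or sensitivity rule for stented patients. Footnote 10 is attached to the standard-of-care bronchoscopy row and not to the separate stenting row, but its wording covers all of Section 6.1.2, where stenting is described. The case report form may therefore lack the detail needed to separate the two kinds of stent.

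**The case against.** The strongest defense is that the exclusion has a sound measurement reason. A stent opens the lumen mechanically, so a later obstruction reading no longer reflects the tumor, and taking it at face value would credit the stent to I-PDT. This stands as a reason not to use the reading. It does not justify dropping the patient, who can stay in the denominator with the outcome set by the reason for the stent.

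A second defense is that obstruction is an unlisted, descriptive measure with no threshold or formal rate. This also stands, and it limits the weight of the point. Because Section 9.1 sits under objective tumor response, a reader might infer that the primary efficacy result is biased. The documents do not support that: the primary test is CR+PR by RECIST, without a stent exclusion.

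Third, a reader might infer that any stent placed after I-PDT marks a treatment failure. That goes too far. The Section 6.1.2 sentence belongs to the Day 0 steps and is followed by stenting to secure the airway. A stent placed in the same session as the light says nothing about a response assessed at 4 weeks (Section 9.2.1) or 12 weeks (Section 12.1.3). Scoring such patients as failures would create a bias in the other direction. For stents placed before or during that session, the direction of the selection is uncertain.

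Two further inferences fail. Bronchoscopy is not the only look at the airway: Section 4.1 also uses a follow-up chest CT to evaluate obstruction, and the number of bronchoscopies is a secondary endpoint. Nor would stent information be lost for good under footnote 10, since procedure notes would probably allow recovery, at the price of chart review across sites.

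**Conclusion.** The point holds for the supportive obstruction measure only. As written, Section 9.1 lets patients stented after the procedure day for residual or recurrent obstruction leave the measure because of its outcome, so the result can be biased upward. If all such patients are failures, the inflation factor is 1/(1−s): 1.11 at 10% stented and 1.25 at 20%. It is smaller if some of them did respond, and nil if stenting is unrelated to response. The actual size cannot be determined from the documents, which give no stent rate, no obstruction response rate and no definition of improvement. The primary CR+PR test, its alpha and its power are unaffected. The change is worth making because it is cheap and is easier to make before the data are collected.

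**What to change.** These are changes to analysis and recording only; no clinical rule changes.

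1. In Section 9.1, state that an obstruction reading from a stented lumen is not used, but that the patient stays in the denominator.
2. Count a stent placed after the Day 0 session for residual or recurrent obstruction of the treated airway as not improved. Section 8.1.6 foresees additional I-PDT after Day 0, so also say how a stent placed in such a session is classed.
3. Report patients stented before or during the Day 0 session as a separate group, not as failures, so that every treated patient is accounted for.
4. Clarify footnote 10 so that the case report form records the date, site and reason for each stent, on Day 0 and during follow-up.
5. Reconcile the obstruction-baseline wording in Sections 4.1 and 9.2.3.

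The cost is a few sentences in Section 9.1, one footnote, an aligned baseline statement and a few form fields. The obstruction result may look less favorable than under the present rule.
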